		EOI ± 15min		x	x															
End of Treatment (EoT) Visit	28 days (± 7) after last dose	At vis t		x	x	x	x													
Safety FU (90d after last dose)		At vis t		x	x	x										x				
In addition, samples to be taken at the following instances:																				
In the event of an IRR ≥ G2 or hypersensitivity event or AE ≥ G3 leading to dose reduction or interruption		At vis t			x	x			x						Any visit					x
		At vis t																		
DLT		At vis t			x	x			x										x	
Unscheduled Visit ⁱ		At vis t			x	x	x	x	x										x	

Table 2 Schedule of Activities Q3W, Details (cont.)

a)	The time windows can be used for flexibility. For example if Day 2 occurs on a Friday, Day 4 can be conducted on the following Monday and Day 8 on the Thursday.
b)	During the course of the study, PK/PD sampling time points may be modified based on emerging data to ensure that PK/PD of RO7296682 can be adequately characterized. In this case, no new additional PK/PD samples will be introduced but sampling times may be modified. Blood for PK/PD should be drawn at the indicated time points.
c)	All blood samples for PK assessments will be collected from an IV line in the opposite arm to the one for drug infusion.
d)	Up to Cycle 5: PK and ADA samples should be taken at indicated time points . Subsequent cycles until 6 months after first dose of RO7296682: PK and ADA samples will be taken on Day 1 of each cycle. Subsequent cycles after first 6 months of RO7296682 treatment: PK and ADA samples will be taken only Day 1 at cycle of tumor assessments .
e)	Unscheduled PK samples will be taken (where feasible) at the time of development of any of the following events, or at the earliest possible convenience thereafter: * DLT * Dose reduction or treatment reduction or interruption due to IRR/CRS event \geq G2 or hypersensitivity event or AE \geq G3. - At time of interruption, collect the unscheduled PK sample and clearly record the reason for this collection (i.e., due to interruption). - At infusion restart and completion, collect scheduled pre, (mid – where applicable) and post infusion time points as noted per SoA.
f)	Tryptase and IgE samples will be collected for local analysis at onset of the reaction. A second sample for central IgE/Tryptase analysis will be collected approximately 48 hours after onset of the reaction.

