4.1.2.1 Part A: Single Agent Dose Escalation

The primary objective of Part A will be to determine the MTD and/or RP2D and DLT profile in multiple participant cohorts. Part A starts with an initial dose of 0.3 mg (see Section 4.3 for dose justification).

[REDACTED]

The DLT period starts from the first administration of RO7296682 and ends 7 days after the second administration of RO7296682. [REDACTED]

The first participant at each dose level must have completed at least 7 days from the first dose without DLT before the second participant can be treated at this dose level. If the first participant experiences a DLT within the first 7 days of treatment, a period of at least 7 days must be maintained between the second and third participants. This pattern must be maintained for subsequent participants until a period of at least 7 days without a DLT has been completed between participants. Once this is achieved, all subsequent participants in a cohort can be enrolled, with no fixed observation period between participants. After the third evaluable participant in each cohort has completed the DLT observation period, the logistic regression model will be updated with the treatment outcome (i.e., the occurrence of DLT) and a new estimate of the MTD will be derived and the recommended dose will be either the new estimate of the MTD or the maximum dose allowed by safety constraints. Selection of the new dose level must be agreed by the Investigator and the Sponsor, as well as being guided by the EWOC recommendation. Please refer to Section 4.1.5 for the communication strategy.

The design will continue as described, assigning participants to the current maximal dose allowed as estimated from all of the DLT data cumulatively, until one of the pre-defined stopping criteria are satisfied (see Section 4.1.4) or the pre-determined sample is reached, whichever comes first.

Built-in safety constraints are in place to prevent exposing participants to undue risk of toxicity:

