4.1.3 Dose-Limiting Toxicities

A DLT is defined as a clinically significant AE (classified according to the NCI CTCAE v.5.0, as applicable) or significant laboratory abnormality if all of the following events apply:

- occurring during the DLT assessment period as defined in Section [4.1.2.1](#); and
- considered to be related to study treatment RO7296682 by the Investigator, and
- is not attributed to disease progression or another clearly identifiable cause

During the dose escalation phase, participants who withdraw before the end of the DLT period, for reasons other than DLTs, and participants who did not receive two doses of RO7296682 will be replaced to ensure that at least 3 DLT evaluable participants have been assessed prior to moving to the next dose level (see Section 7.1 for replacement rules). The DLT will be counted for each dose separately and each participant will contribute one single representative data point to the EWOC design.

The following AEs are considered DLTs:

Hematological toxicities defined as:

- Grade 4 neutropenia (ANC of $<500/\mu\text{L}$) lasting ≥ 7 days
- Grade ≥ 3 febrile neutropenia
- Grade 4 thrombocytopenia lasting ≥ 48 hours
- Grade 3 thrombocytopenia associated with significant bleeding episode and/or bleeding episodes requiring platelet transfusions
- Grade 4 anemia

Any non-Hematological toxicities Grade ≥ 3 except for:

- Grade 3 nausea, vomiting, or diarrhea that resolves to Grade ≤ 1 with or without treatment and which resolves within one week
- Grade ≥ 3 fatigue that resolves to Grade ≤ 2 within 7 days
- Grade 3 arthralgia that can be adequately managed with supportive care or that resolves to Grade ≤ 2 within 1 week
- Fever >40 degrees Celsius that occurs within 48 hours of RO7296682 infusion and resolves to $<$ Grade 2 within 48 hours and is fully resolved within 7 days
- Grade ≥ 3 laboratory abnormality that is asymptomatic and deemed by the Investigator not to be clinically significant
- Grade 3 autoimmune thyroiditis or other endocrine abnormality that can be managed by endocrine therapy or hormonal replacement
- Grade 3 tumor flare defined as local pain, irritation, or rash localized at sites of known or suspected tumor

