6.6 DOSE MODIFICATION

Instructions for RO7296682 administration, change of infusion rate, interruption of infusion, discontinuation of RO7296682 treatment, and management of specific RO7296682-related AEs are provided in Section 6.1, Section 7, and Section 8.3.8.

Dose-Limiting Toxicities (DLTs):

Participants who experience toxicities fulfilling the definition of a DLT while on treatment should be discontinued from study treatment. Nevertheless, the Investigator, after discussion with the Sponsor, will have the option to reduce the dose of RO7296682 to the previous tolerated dose level, if participant is deemed to be deriving clinical benefit.

RO7296682-related Adverse Events:

AEs attributable to RO7296682 must resolve to Grade 1 or baseline before resuming treatment. Exceptions may be allowed after a careful potential clinical risk/benefit assessment by the Investigator and approval by the Medical Monitor.

Dose reductions may be allowed with the approval of the Medical Monitor.

Adverse Events not attributed to study treatment:

A delay of RO7296682 administration for up to two cycles will be acceptable to allow for resolution of toxicity to NCI CTCAE Grade ≤ 2 for hematological toxicities or Grade ≤ 1 for non-hematological toxicities. If in the judgment of the Investigator, a participant is likely to derive clinical benefit from RO7296682 after a hold of more than 2 doses, study drug may be re-started with the approval of the Medical Monitor

Liver Function Test (LFT):

For participants with documented liver metastasis and elevated liver function test (LFT) results at baseline, further elevations of LFT results may not require dose interruptions if there are no progressive changes in the ALT and/or AST (less than a doubling) and if there are no progressive elevations in total bilirubin or international normalized ratio (INR).

Investigators are encouraged to contact the Sponsor for further guidance if needed. After Cycle 1 is completed, dose modifications should be discussed with the Sponsor.

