9.3 POPULATIONS FOR ANALYSES

For purposes of analysis, the following populations are defined in [Table 12](#).

Table 12 Analysis Populations

Analysis Population	Description
Efficacy	All participants who received at least one dose of RO7296682, and who have at least one baseline and one on-study tumor assessment. Participants who received at least one dose of study drug and discontinued the study because of progression before the first on-study tumor assessment will be considered as response-evaluable.
DLT evaluable	DLT evaluable participants are those who have completed the DLT period with two administrations of RO7296682 during the DLT period and without DLT, or participants reported with a DLT. This population will be used in the determination of the MTD and/or RP2D.
Safety	All participants randomized to study treatment (RO7296682) and who received at least one dose of the study treatment, whether prematurely withdrawn from the study or not, will be included in the safety analysis.
Pharmacokinetic	All participants who have received at least one dose of study treatment (RO7296682) and who have data from at least one post-dose sample will be included in the PK analysis population. Participants will be excluded from the PK analysis population if they significantly violate the inclusion or exclusion criteria, deviate significantly from the protocol, or if data are unavailable or incomplete which may influence the PK analysis. Excluded cases will be documented together with the reason for exclusion. All decisions on exclusions from the analysis will be made prior to database closure.
Immunogenicity	The immunogenicity analyses will include all participants with at least one ADA assessment, irrespective of whether or not the participant receives any treatment. Excluded cases will be documented together with the reason for exclusion.

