9.4.3 Safety Analyses

Unless otherwise specified all safety analyses listed in [Table 14](#) will be based on the safety population. All safety parameters will be analyzed using descriptive statistics, summarized and presented in tables. Data will be summarized by dose and regimen (if applicable) within each part.

Table 14 Safety Statistical Analysis Methods

Endpoint	Statistical Analysis Methods
Adverse events	The original terms recorded on the eCRF by the Investigator for AEs will be coded by the Sponsor. Adverse events will be summarized by mapped term and appropriate thesaurus level. The severity of AEs will be graded according to the NCI CTCAE v5.0. Toxicity grade, seriousness, and relationship to study treatment will be presented, as well as summaries of deaths, AEs leading to death and premature withdrawal from study treatment. A glossary of AEs, medication(s), and procedures will be provided.
Clinical laboratory tests	All clinical laboratory data will be stored in the database in the units in which they were reported. Laboratory test values will be presented in International System of Units (SI units; Système International d'Unités) by individual listings with flagging of abnormal results.
Vital signs	Vital signs data will be presented by individual listings with flagging of values outside the normal ranges and flagging of abnormalities. In addition, tabular summaries will be used, as appropriate.
ECG data analysis	ECG data will be presented by individual listings. In addition, tabular summaries will be used, as appropriate.
Concomitant medications	The original terms recorded on the participant's eCRF by the Investigator for concomitant medications will be standardized by the Sponsor by utilizing a mapped term and appropriate drug dictionary level. Concomitant medications will be presented in summary tables and listings.
Nature and frequency of DLTs	DLT events will be presented by individual listings. The MTD will be estimated with an mCRM-EWOC using DLT evaluable participants. The MTD estimate will be presented along with 90% Credible Intervals.

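### A DLT-free participant is evaluable after two administrations whatever dose was given, so a reduced second dose can count as a non-DLT at the assigned dose

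*Combined protocol and SAP*

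**What the plan says.** - **Evaluability.** Section 9.3, Table 12: "DLT evaluable participants are those who have completed the DLT period with two administrations of RO7296682 during the DLT period and without DLT". Participants reported with a DLT are evaluable in any case.
- **Use.** Section 9.4.3, Table 14: "The MTD will be estimated with an mCRM-EWOC using DLT evaluable participants". The MTD and/or RP2D is part of the primary objective.
- **Replacement.** Section 4.1.3: "participants who did not receive two doses of RO7296682 will be replaced". Section 7.1 lists participants who fail to complete the DLT period for reasons unrelated to the drug, and excludes major protocol violators from the DLT population.
- **Window.** Section 4.1.2.1: "The DLT period starts from the first administration of RO7296682 and ends 7 days after the second administration of RO7296682". Redacted text follows this sentence.
- **Reductions.** Section 6.6, on drug-related adverse events: "Dose reductions may be allowed with the approval of the Medical Monitor". The same section ends: "After Cycle 1 is completed, dose modifications should be discussed with the Sponsor". Section 1.3, Table 2, footnote e, provides PK sampling for "Dose reduction or treatment reduction or interruption due to IRR/CRS event" of Grade 2 or higher, among other events.
- **Model input.** Section 4.1.3: "The DLT will be counted for each dose separately and each participant will contribute one single representative data point to the EWOC design".

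**The concern.** Evaluability depends on the number of administrations and not on the dose given. A second dose may be reduced, with approval, while the participant is still in the DLT window, and nothing visible removes or re-scores that participant.

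Such cases are not a random subset. A reduction under section 6.6 for a related event happens in someone who has already shown some intolerance. Section 4.1.3 exempts several Grade 3 events from the DLT definition, so appreciable related toxicity can precede a reduced second dose without a DLT being recorded. If that participant is scored as DLT-free at the assigned dose, the model is told that the dose was tolerated for two cycles when it was given for one. The participant can also complete the three needed for the model update. At stake is the dose-toxicity curve behind the escalation decisions and the MTD.

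**Working it through.** The plan states no figure that depends on this definition. The Part A maximum of about 90 is a cap, and the simulations behind it are redacted. The check is therefore a reading of the text, followed by an illustration of direction.

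**Step 1: follow one participant through the rules.**

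| Stage | Rule | Result |
|---|---|---|
| Related event after dose 1, below the DLT definition | 4.1.3 | No DLT |
| Dose 2 reduced with Medical Monitor approval | 6.6 | Permitted; no exception for the DLT window |
| Seven days pass after dose 2 without a DLT | 4.1.2.1 | DLT period completed |
| Two administrations, no DLT | Table 12 | Evaluable |
| Two doses received | 4.1.3 | Not replaced |
| Period completed; reduction permitted and drug-related | 7.1 | Neither visible provision clearly applies |
| One data point supplied | 4.1.3, Table 14 | Enters the mCRM-EWOC; dose label not stated |

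The last row is the open one. DLTs are counted per dose and each participant gives one point, but the text does not say which dose that point carries when doses 1 and 2 differ. The assigned dose is one available reading.

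**Step 2: direction.** Let p be the DLT risk at full exposure and r·p the risk in one under-dosed participant, with r between 0 and 1. For a cohort of three:

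P(0 DLTs) = (1 − p)² × (1 − r·p)

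| Assumed p | r = 1 (same risk) | r = 0.5 | r = 0 |
|---|---|---|---|
| 0.25 | 0.422 | 0.492 | 0.562 |
| 0.33 | 0.301 | 0.375 | 0.449 |
| 0.40 | 0.216 | 0.288 | 0.360 |

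For example, at p = 0.33 and r = 0.5: 0.67² × 0.835 = 0.375. If risk does not fall with exposure, nothing changes. Otherwise a clean cohort becomes more likely than it should be.

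**Step 3: effect on an overdose probability.** This uses a single-cohort beta-binomial, not the trial's two-parameter logistic model. The 0.33 threshold and the priors are assumptions. For Beta(1,1) and no DLTs in n, P(rate > 0.33) = 0.67^(n+1), so 0.67⁴ = 0.20 for n = 3 and 0.67³ = 0.30 for n = 2.

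| Assumed prior | 0/3 (kept) | 0/2 (excluded) |
|---|---|---|
| Beta(1,1) | 0.20 | 0.30 |
| Beta(0.5,0.5) | 0.11 | 0.18 |
| Beta(0.3,0.7) | 0.05 | 0.09 |

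The 0/2 column gives the under-dosed participant no weight at all. That overstates the effect, because dose 1 was given in full.

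**The case against.** Several points on the other side stand.

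- **Dose label.** A reader might infer that the participant is entered as a full-dose non-DLT. No visible text says so. The wording on the single representative point leaves the dose open, and the redacted text in 4.1.2.1, or the redacted model description in 4.1.2, could settle it.
- **Stopped infusions.** A reader might infer that an abandoned infusion counts as an administration. The term is undefined, and footnote e describes interruption followed by restart and completion. This is a gap in definition, not a stated rule.
- **Size of the reduction.** Section 6.6 mentions the previous tolerated level only for participants with a DLT, who are evaluable anyway. For other related events no size is given, so no lost fraction of exposure can be stated.
- **Crossing a limit.** Under the flat prior the illustration passes a 25% overdose limit, which is itself an assumption. Under the other two priors it does not.
- **Escalation step.** The 3-fold increment in 4.1.2.1 depends on no DLT having been observed. Excluding a DLT-free participant does not remove it; only a DLT in the replacement would.
- **Existing review.** Escalation meetings see dose-administration data for each participant (4.1.5), the SDEC can override the model (4.2), and an investigator may class a significant related toxicity as a DLT (4.1.3). These are real protections for the decision, but they are discretionary and do not determine which data enter the model.
- **Selection.** Replacing participants who showed intolerance can itself favour tolerant ones. The fix has to guard against this.

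**Conclusion.** The point holds as a defect in the evaluability definition. Followed as written, Table 12 and section 4.1.3 keep a DLT-free participant with a reduced second dose in the MTD population and in the minimum of three, and do not say which dose the outcome belongs to. That the outcome is always credited to the full assigned dose is not shown; that it can be is enough to warrant a change.

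If DLT risk does not decrease with exposure, crediting it to the assigned dose leaves apparent toxicity there unchanged or lowers it. The size for this trial is unknown, since the prior, target and overdose limit are not visible; the figures above show direction only. The conclusion also depends on no rule in the redacted text covering the case. If one exists, Table 12 and 4.1.3 should still refer to it.

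**What to change.** 1. In Table 12 and section 4.1.3, make a DLT-free participant evaluable only if both administrations in the DLT period were at the assigned cohort dose. Add a minimum fraction of each planned infusion, set by the sponsor, so that trivial losses do not disqualify anyone.
2. State which dose the model uses when a participant's two doses differ.
3. Align section 7.1, whose replacement wording for an incomplete DLT period covers only reasons unrelated to the drug.
4. Before replacing such a participant, review the case at the dose-escalation meeting against the existing investigator-judgement DLT clause in 4.1.3. Report excluded participants with reasons, and run the model once with them included.
5. Keep every participant with a DLT evaluable, whatever was received.

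The cost is a few sentences in three places, one extra model run when a case arises, and an occasional additional replacement in Part A. The change concerns the analysis population only; the dose-modification rules for participants stay as they are.

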9.4 STATISTICAL ANALYSES

The data will be analyzed by the Sponsor and/or designated contract research organization (CRO). Any data analysis carried out independently by the Investigator should be submitted to the Sponsor before publication or presentation. The data will be summarized with respect to demographic and baseline characteristics, efficacy observations and measurements, safety observations and measurements, and PK and biomarker measurements. The baseline value of any variable will be defined as the last available value prior to the first administration of study drug.

9.4.1 Demographics and Baseline Characteristics

Demography and baseline characteristics (including age, sex, participant disposition, previous therapies, and medical history) will be analyzed using descriptive statistics. The

analysis will be based on the safety analysis population. Data will be summarized by dose cohort and regimen within each part.

This is a one group, monotherapy dose escalation study; therefore comparability of treatment groups does not apply.

9.4.2 Efficacy Analyses

The primary and secondary efficacy analyses listed in [Table 13](#) will include all participants in the efficacy population with participants grouped according to dose cohort (and schedule if applicable) within each study part.

Table 13 Efficacy Statistical Analysis Methods

Endpoint	Statistical Analysis Methods

According to RECIST Version 1.1 criteria (Appendix 7) and iRECIST (Appendix 8)
 
 • Objective response rate (ORR) • Disease control rate (DCR) • Duration of response (DoR) • On treatment progression free survival (PFS) 	
No formal statistical model and no formal hypothesis testing are planned in this study. Tumor response data will be reported using descriptive statistics. Response data will be listed. Participants with missing or no response assessments will be classified as not evaluable unless there is documented clinical deterioration, in which case participant will be classified as non-responders. Reasons for the non-evaluability will be summarized (e.g., withdrawal of consent, study discontinuation because of AE or physician decision). ORR and DCR will be summarized by using relative frequencies and 90% confidence interval (CI). Duration of response and PFS (on-treatment) will be summarized by using time-to-event analyses and Kaplan-Meier curves.

 • Overall Survival (OS) (if available) 	
OS data may be tabulated and summarized using time-to-event analyses and Kaplan-Meier curves if data are collected and mature.
 
Summaries will be carried out by cohort (and schedule if applicable) separately for each part.

Objective response rate (ORR) is determined as the rate of participants with an overall response of CR or PR. Disease control rate is determined as the rate of participants with an overall response of either CR, PR, or SD rate. ORR and DCR will be derived for RECIST Version 1.1 and will be based on Investigators' assessment. Objective response (OR) is defined as a CR or PR as determined by the Investigator. For this protocol, confirmation of response is required at least 4 weeks after a first response occurred. To classify a response as SD, measurements will have to be classified as stable (according to RECIST Version 1.1) at least once after study entry at a minimum of 6 weeks after study entry. Participants with missing or no response assessments will be classified as not evaluable unless there is documented clinical deterioration, in which case participant will be classified as non-responders.

DoR will be calculated for participants who have a best overall response of CR or PR and will be defined as the time from first occurrence of a documented OR until the time of documented disease progression or death (death within 30 days from last study

treatment) from any cause, whichever occurs first. Censoring methods will be the same as the one applied for progression-free survival (on-treatment PFS).

PFS on treatment will be defined as the time from study treatment initiation (C1D1) to the first occurrence of documented disease progression (based on RECIST Version 1.1 Investigator's assessment) or death from any cause, whichever occurs first. For participants who do not have documented progressive disease or death (within 30 days from last study treatment) during the study, PFS will be censored at the day of the last tumor assessment. Participants without any post baseline assessments or with all post-baseline assessments having unknown result/response but known to be alive at the clinical cut off for the analysis will be censored at the date of study treatment initiation plus one day.

Sensitivity analyses of response endpoints (ORR, DRC, DoR, and PFS) may include the evaluation of response according to iRECIST. As a sensitivity analysis, the analysis described in [Table 13](#) may be applied to a more generic definition of PFS that also includes deaths occurring more than 30 days after last study treatment. Secondary analyses of response endpoints may (if implemented) include the evaluation of response.

OS is defined as the time from the first dose of study treatment to the time of death from any cause. Participants who are still alive at the time of analysis will be censored at the time of their last study assessment (for active participants) or at the last date known alive (for participants in follow-up).

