9. LACK OF EFFICACY OR WORSENING OF TUMOR

Events that are clearly consistent with the expected pattern of progression of the underlying disease should not be recorded as adverse events. These data will be captured as efficacy assessment data only. In most cases, the expected pattern of progression will be based on RECIST Version 1.1. In rare cases, the determination of

clinical progression will be based on symptomatic deterioration. However, every effort should be made to document progression using objective criteria. If there is any uncertainty as to whether an event is due to progressive disease, it should be reported as an adverse event.

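### Participants kept in the efficacy population because they stopped for progression before any scan are censored for PFS at treatment start plus one day

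*Combined protocol and SAP*

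**What the plan says.** Table 12 (Section 9.3) builds the efficacy population from dosed participants with a baseline and at least one on-study tumor assessment. It makes one exception: dosed participants who "discontinued the study because of progression before the first on-study tumor assessment will be considered as response-evaluable". Section 9.4.2 states that the efficacy analyses, PFS among them, "will include all participants in the efficacy population with participants grouped according to dose cohort".

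The PFS event in Section 9.4.2 is the "first occurrence of documented disease progression (based on RECIST Version 1.1 Investigator's assessment) or death from any cause". Participants who "do not have documented progressive disease or death (within 30 days from last study treatment) during the study" are censored at their last tumor assessment. A separate rule covers those with no post-baseline assessment, or with only unknown results, who are known to be alive at the clinical cut-off: they "will be censored at the date of study treatment initiation plus one day". That rule makes no exception for someone who stopped because of progression.

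For response rate and disease control rate, participants without a response assessment are "classified as not evaluable unless there is documented clinical deterioration, in which case participant will be classified as non-responders".

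**The concern.** A participant who leaves treatment because the disease is progressing, before the week-8 scan, has one of the worst outcomes in the trial. Table 12 recognises this by keeping that person evaluable. The PFS rule then treats the same person as someone about whom nothing is known after the first day. Such censoring is informative: the reason for the missing scan is the outcome being measured. The Kaplan-Meier curve takes no step for these participants, and their experience is in effect replaced by that of people who lasted long enough to be scanned. The bias is upward. PFS is reported by dose cohort, and a Part A cohort may have only three DLT-evaluable participants, so a single such person can change a cohort's curve visibly.

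**Working it through.** The plan gives no expected PFS, event count or power (Section 9.1 states that no hypothesis test is planned), so there is no figure of its own to reproduce. The check has two parts.

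**Reading the rules together**

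1. PFS uses the efficacy population (Section 9.4.2).
2. In that population, a participant with no on-study assessment can be present only through the Table 12 exception, that is, by discontinuing because of progression.
3. Therefore, within the PFS analysis, the no-assessment part of the censoring rule reaches only those participants, if alive at cut-off. The part on unknown results covers different people.
4. They have no qualifying event. PFS needs RECIST v1.1 progression. Appendix 7, Section 2.4.3 treats symptomatic deterioration as a reason for stopping therapy and not as a response category.
5. No later scan is required. Notes o and r to the Schedule of Activities (Table 1) ask for end-of-treatment and safety follow-up scans from those who stopped for reasons other than progression.
6. The two PFS sensitivity analyses named in Section 9.4.2 are both optional. One applies iRECIST; the other adds deaths more than 30 days after last treatment. Neither captures a living participant with clinical progression and no scan.

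**Size**

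Inputs from the protocol: at most 50 participants in Part B (Section 9.2), at least 3 DLT-evaluable participants per Part A cohort (Section 4.1), and a first scan at week 8 (Table 1, note o). The maximum of 50 is used as n, although the efficacy population could be smaller.

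Assumptions not in the protocol: k affected participants; an event date of day 28 if they were counted; 40% of those at risk progressing at each 8-week scan, rounded to whole people; a cohort of 6 as a further example; no other censoring before day 28.

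Let r of the n-k remaining participants be event-free after the week-8 scan.

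- As written: the k leave before the first event, so PFS = r/(n-k).
- Counted as events: PFS = [(n-k)/n] × [r/(n-k)] = r/n.
- Ratio: n/(n-k). From day 28 onward both analyses have the same risk sets, so the ratio carries through the rest of the curve.

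| n | k | r | As written, r/(n-k) | As events, r/n | n/(n-k) |
|---|---|---|---|---|---|
| 50 | 1 | 29 | 0.592 | 0.580 | 1.02 |
| 50 | 3 | 28 | 0.596 | 0.560 | 1.06 |
| 50 | 5 | 27 | 0.600 | 0.540 | 1.11 |
| 50 | 10 | 24 | 0.600 | 0.480 | 1.25 |
| 6 | 1 | 3 | 0.600 | 0.500 | 1.20 |
| 3 | 1 | 1 | 0.500 | 0.333 | 1.50 |

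With 30% or 50% progressing per scan the ratio is unchanged. At 40%, the median for n = 50 is day 112 under both treatments for k = 1, 3 and 5. For k = 10 it is day 112 as written and day 56 with the k counted as events.

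**The case against.** The strongest reply is that RECIST v1.1 PFS is the declared endpoint (synopsis and Table 3), and that censoring a participant without a RECIST assessment is what such a definition implies. Making clinical progression a main PFS event would conflict with Table 3 and Appendix 7, and would add a subjective event to an open-label, investigator-assessed endpoint. That stands, and it is why the main definition should not change.

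The affected group is also narrow. Appendix 3, Section 9 describes progression determined by symptoms as rare. That section and Appendix 7 both press for objective documentation, and Section 8.1.1 allows a repeat CT whenever progression is suspected. Deaths within 30 days of last treatment remain events, and so does RECIST progression on a later scan. All of this limits k; none of it supplies an event for a living participant who is never scanned.

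Finally, PFS is secondary and descriptive, and Section 4.1 bases the MTD or RP2D on safety, tolerability and PK/PD. Section 9.4.2 also lists response data and summarises reasons for non-evaluability. This lowers the stakes, but a listing does not correct the curve.

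A reader might go further and infer that the plan itself labels these participants as progressors. It does not. Table 12 calls them response-evaluable, and they are non-responders only where clinical deterioration is documented; otherwise they are not evaluable. The disagreement with the response endpoints is therefore one of treatment, and is not a recorded progression that PFS ignores.

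**Conclusion.** The point holds as an inconsistency between Table 12 and the PFS censoring rule, with a known direction and an exact factor. Compared with counting them as events, k affected participants among n inflate later PFS estimates by n/(n-k): 2% to 25% for 1 to 10 of 50, 20% for one of six, 50% for one of three. The factor assumes no other censoring before the affected participants' event dates. The number k is assumed throughout; the documents give no rate and suggest a small one.

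Two wider readings are not supported. A reader might infer that a comparison of PFS between doses is distorted, but none is planned: Section 9.4.2 only groups by cohort, and Section 9.4.1 says that comparability of treatment groups does not apply. A reader might also extend the point to someone who has a scan without progression and then stops for clinical deterioration. Censoring that person at the last assessment is ordinary practice under a RECIST-only definition and does not contradict Table 12.

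**What to change.** Reconcile Section 9.3 with Section 9.4.2 and keep RECIST v1.1 PFS as the main definition. In Section 9.4.2, pre-specify a sensitivity PFS analysis in which discontinuation because of progression, without a post-baseline scan, is an event on the date of documented progression or, if that is not recorded, on the date of discontinuation. Report by cohort the number of participants censored at C1D1 plus one day, with the reason for each.

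The cost is a wording change, one more analysis and one small table, with no new visits or procedures. Section 7.1 already puts the primary reason for stopping treatment on the eCRF, but it does not mention a date of clinical progression, so the sponsor should confirm which date is captured. The downside is a second PFS estimate that may look slightly less favourable.
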